9.4.2 Efficacy Analyses

Primary Endpoint

The change from baseline in MADRS scores will be summarized separately by treatment arm for each visit. Associated baseline scores will be taken as the last corresponding measurement prior to the first dose of IMP in the treatment period (i.e., Visit 2, predose).

The primary endpoint of change from baseline MADRS total score at 24 hours post start of infusion will be evaluated using a mixed effects model for repeated measure (MMRM) analysis with observed cases only. The MMRM model will include fixed effects for treatment group, region, visit, study site and treatment group by visit interaction, with subject as a random effect and baseline score as a covariate. An unstructured covariance matrix will be used to estimate the variance-covariance structure within subjects across time points. If convergence is not obtained, then other covariance structures to be used will be specified in the SAP. Objective criteria for assessing normality assumptions and proposed alternative analyses will be specified in the SAP.

From this analysis the least squares (LS) mean estimates for each treatment arm at each visit, along with the standard error and 95% confidence intervals (CIs) will be presented separately. In addition, estimates of the treatment difference at each visit will be presented along with standard errors of the difference and 95% CIs. The primary comparison for the MADRS is the estimate of the treatment difference at 24 hours after the start of the infusion.

Secondary endpoints

The change from baseline to Day 14 in MADRS, HAM-D, GAD-7 and QIDS-SR scores will be analyzed using similar model approaches as for MADRS. Observed and change from baseline values in continuous secondary endpoints will be summarized descriptively by treatment group. Continuous secondary efficacy endpoints assessed at more than 1 postbaseline visit will be analyzed using an MMRM analysis. The MMRM model will include fixed effects for treatment group, region, visit, study site and treatment group by visit interaction, with subject as a random effect and baseline score as a covariate.

From this analysis the LS mean estimates for each treatment arm at each visit, along with the standard error and 95% CIs will be presented separately. In addition, estimates of the treatment

difference at each visit will be presented along with standard errors of the difference and 95% CIs.

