Within a single analysis timepoint per patient, if $\geq 25\%$ of items used to calculate a total score for a given scale are missing, the total scale score for that patient and timepoint will be considered missing.

If $<25\%$ of items are missing, the total score will be calculated (prorated) as the arithmetic mean of non-missing items multiplied by the total expected number of items and rounded up to the nearest integer.

Additionally, separate sensitivity analyses will be performed with missing MADRS data imputed with a multiple imputation method. The multiple imputation (MI) method assumes a missing-at-random (MAR) data missing pattern. Imputation will be performed using the Fully Conditional Specifications parametric regression model. A total of 50 imputations will be generated using PROC MI. For each of the 50 datasets, missing MADRS total score will be imputed using the regression model, as implemented in the PROC MI with the following variables considered (as given on the VAR statement): Treatment, Region, Baseline MADRS and each subsequent post-baseline MADRS score. Response status (Yes, No) and revised change from baseline values will be derived in each MI dataset based on the newly imputed data. The seed to be used in this MI model is 60773.

Example SAS code for PROC MI is as follows:

```
PROC MI DATA=MI NIMPUTE=50 SEED=&SEED. OUT=MI1 ROUND=1 MINIMUM=0;
  CLASS TRTP REGION1;
  VAR TRTP REGION1 ATPTN20 ATPTN40 ATPTN50 ATPTN70 ATPTN80
  ATPTN90;
  FCS REG (ATPTN20 = TRTP REGION1);
```

```
FCS REG (ATPTN40 = TRTP REGION1 ATPTN20) ;
FCS REG (ATPTN50 = TRTP REGION1 ATPTN20 ATPTN40 ) ;
FCS REG (ATPTN70 = TRTP REGION1 ATPTN20 ATPTN40 ATPTN50) ;
FCS REG (ATPTN80 = TRTP REGION1 ATPTN20 ATPTN40 ATPTN50
ATPTN70 ) ;
FCS REG (ATPTN90 = TRTP REGION1 ATPTN20 ATPTN40 ATPTN50
ATPTN70 ATPTN80) ;
RUN;
```

Note: TRTP = randomized treatment group, REGION1 = region (US/Europe). Note: Each of the ATPTNxx variables represent the MADRS score at each analysis timepoint (Pre-dose, 2 hours, 4 hours, 24 hours, Day 8 and Day 15).

The imputation models may be modified based on the actual data if there is an issue in model convergence. If the missingness at the MADRS 24 hour timepoint is >5%, additional analyses exploring missing-not-at-random (MNAR) assumptions will be performed.

F. Primary Efficacy Outcome Analysis

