The primary objective endpoint of change from baseline MADRS total score at 24 hours post start of infusion will be tested with a 1-sided test of equivalence in means at 0.025 significance level, a mixed model repeated measures (MMRM) model will be used to analyze the change from baseline values using fixed effects of treatment group, analysis visit, region and treatment group-by-visit interaction. The baseline value will be included as a covariate. An unstructured covariance matrix will be used to model the within-patient variance-covariance errors. A random effect of subject will be included. If the unstructured covariance structure matrix results in a lack of convergence, the heterogenous first-order autoregressive covariance structure will be used as the first alternative, followed by the compound symmetry covariance structure. The Kenward-Roger approximation will be used to estimate the denominator degrees of freedom. Any missing data are assumed to be missing at random. . The hypothesis is defined as follows:

$$H_0: \Delta_{\text{active}} - \Delta_{\text{placebo}} = 0 \quad \text{vs} \quad H_1: \Delta_{\text{active}} - \Delta_{\text{placebo}} < 0$$

where

- Δ_{active} : Mean change from baseline MADRS total score at 24 hours after start of infusion (Test)
- Δ_{placebo} : Mean change from baseline MADRS total score at 24 hours after start of infusion (Reference)

Model-based adjusted means for each treatment group, pairwise adjusted differences with placebo (reference), 95% CI for the differences and the associated p-values will be presented at each analysis visit. Each PCN-101 dose will be compared with placebo. An example of the SAS code is provided below:

```
proc mixed data=data;    class USUBJID
AVISITN TRTPN SITEID;
  model CHG = BASE REGION1 AVISITN TRTPN AVISITN*TRTPN/s cl ddfm=kr;
  repeated AVISITN / TYPE=UN SUB=USUBJID;    lsmeans AVISITN * TRTPN /
  diff; run;
```

Since subjects are confined to the clinic at the time of the primary endpoint, it is anticipated that missing data will be infrequent. No imputation will be applied for this primary efficacy analysis but missing data assumptions will be explored in sensitivity analyses.

The described analysis will be performed on the FAS.

G. Primary Efficacy Sensitivity Analysis

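### The text of the primary MMRM adds a random subject effect to an unstructured covariance: one parameter too many, and not the model in the SAP's own example code

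*SAP*

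**What the plan says.** SAP VII.F (Primary Efficacy Outcome Analysis) sets the residual structure: "An unstructured covariance matrix will be used to model the within-patient variance-covariance errors". It then adds: "A random effect of subject will be included".

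Protocol 9.4.2 has the same combination. The model is fitted "with subject as a random effect and baseline score as a covariate", and "An unstructured covariance matrix will be used to estimate the variance-covariance structure within subjects across time points". The protocol synopsis (section 1.1, table under Efficacy Analyses) repeats the random subject effect for the primary and the secondary models.

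The PROC MIXED code in SAP VII.F is labelled as an example. It contains "repeated AVISITN / TYPE=UN SUB=USUBJID" and no RANDOM statement.

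The same SAP section gives the rule for leaving the unstructured model. The only trigger is non-convergence of that model. The order of replacement is then fixed: "the heterogenous first-order autoregressive covariance structure will be used as the first alternative, followed by the compound symmetry covariance structure".

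Neither document says whether the text or the code governs, whether the random effect stays in the fallback models, or whether a singular-matrix warning counts as lack of convergence.

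**The concern.** An unstructured matrix already holds every possible within-subject variance and covariance. A random intercept adds one constant to all of its elements, and no data can separate that constant from the matrix itself. The likelihood is therefore flat in one direction. A fit of the text model may stop with a convergence failure or a singular Hessian for a reason that has nothing to do with the data.

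Lack of convergence is the SAP's only trigger for moving to ARH(1) and then to compound symmetry. Two analysts working from the same SAP, one from the text and one from the code, could therefore report the primary standard error from different covariance structures. A pre-specified primary analysis should not leave that open. SAP VII.G and VII.H reuse the primary model specification, so the same ambiguity reaches the sensitivity analyses and the secondary MMRM analyses.

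**Working it through.** **1. The plan's own figure.** Protocol 9.2 and SAP III.C give 31 per arm, difference 8, SD 11 and two-sided alpha 0.05.

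- Standard error = 11 × √(2/31) = 2.794.
- Noncentrality = 8 / 2.794 = 2.863; critical t on 60 df = 2.000.
- Power = 80.4% (81.7% by the normal approximation). The stated 80% is reproduced. A one-sided test at 0.025 gives the same figure.

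**2. Parameter count.** SAP VII.E lists the MADRS timepoints as "Pre-dose, 2 hours, 4 hours, 24 hours, Day 8 and Day 15", so five are post-baseline. Write the marginal covariance as V = R + σ²_b J, where R is the residual matrix, σ²_b the subject variance and J the 5 × 5 matrix of ones. V has 5 × 6 / 2 = 15 distinct elements. Replacing (R, σ²_b) by (R + cJ, σ²_b − c) leaves V unchanged. The rank of the map from parameters to V was checked numerically.

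| Structure plus random intercept | Parameters | Rank |
|---|---|---|
| Unstructured | 15 + 1 = 16 | 15 |
| ARH(1) | 6 + 1 = 7 | 7 |
| Compound symmetry | 2 + 1 = 3 | 2 |

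The unstructured matrix alone has 15 parameters and rank 15. The last fallback has the same defect as the main model if the random effect is kept in it; ARH(1) does not.

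**3. Does the redundancy change the result when a fit is obtained?** One data set of 93 subjects × 5 visits was simulated. The subject variance was moved from 0 to 30, with the unstructured part absorbing the change. The −2 REML value (2326.2459), the 24-hour contrast (−1.0137) and its standard error (2.7970) did not move.

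**4. Size if ARH(1) is used instead.** The documents give no visit SDs or correlations for post-baseline MADRS, only the SD of 11 used for the sample size. What follows is therefore assumed, for complete data and for ARH(1) without a random effect. The ARH(1) matrix W closest to the true V minimises log|W| + trace(W⁻¹V). The ratio r is its 24-hour SD divided by the true one, and power is the probability that a noncentral t (60 df, noncentrality 2.863) exceeds 2.000 × r. The ratios below were the same with SD 11 at all visits and with 7/8/11/12/12 at 2 h/4 h/24 h/Day 8/Day 15.

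| Assumed true correlation | r | Power |
|---|---|---|
| Exchangeable (0.5 or 0.7) | 1.00 | 80% |
| AR(1), 0.7 | 1.00 | 80% |
| Uneven: 2 h with 4 h 0.8; Day 8 with Day 15 0.7; any visit with 24 h 0.5; Day 1 with follow-up 0.4 | 1.11 | 74% |
| Uneven: as above, but 0.9 for the two close pairs | 1.24 | 65% |

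**5. Size if compound symmetry is used.** It pools the variance over visits, so for complete data r = √(mean visit variance / 24-hour variance), and the actual two-sided alpha is 2 × [1 − Φ(1.96 r)]. For example, SDs of 7/8/11/12/12 give a mean variance of (49 + 64 + 121 + 144 + 144)/5 = 104.4, so r = √(104.4/121) = 0.93 and alpha = 6.9%.

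| Assumed SDs (2 h/4 h/24 h/Day 8/Day 15) | r | Alpha |
|---|---|---|
| 11 at all visits | 1.00 | 5.0% |
| 9/10/11/11.5/12 | 0.98 | 5.5% |
| 7/8/11/12/12 | 0.93 | 6.9% |
| 7/8/11/10/10 | 0.85 | 9.7% |
| 10/11/11/13/14 | 1.08 | 3.4% |

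In the last row, power falls from 82% to 77% (normal approximation).

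**The case against.** The strongest reply is that the only executable specification in the SAP is sound. The code models within-subject correlation through the residual matrix alone, and the random-effect sentence may be loose wording for repeated measures clustered by subject. This stands as a limit on the harm: if the code is run, this cause triggers no fallback. It does not settle the matter, because the code is offered as an example and the text is explicit in both documents.

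A reader might infer that the primary analysis is bound to fail or to be biased. The documents do not support that. Software may set the redundant variance to zero, or converge with a warning, and step 3 shows that the 24-hour contrast and its standard error are then the same. No failing fit has been shown; failure is possible, not certain.

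A reader might also infer that the defect leads to compound symmetry and an inflated type I error. That does not follow either. ARH(1) comes first and is identifiable even with the random intercept, so compound symmetry needs a second, unrelated failure. Even then the error rate can move in either direction.

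**Conclusion.** Wrong as written, with a limited consequence. The certain part is algebra and comparison of text: the written model is over-parameterised by exactly one, and it conflicts with the example code. The conditional part is the effect on the primary standard error. It is nil if the code is run or if a fit of the text model is obtained.

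If the text model fails and ARH(1) takes over, the 24-hour standard error is right under exchangeable or AR(1) correlation. It is about 1.1 to 1.2 times too large under the uneven correlations assumed here, with power of about 65-75% instead of 80%. If ARH(1) also failed, compound symmetry would give a two-sided alpha of about 3% to 10% across the assumed SDs, and exactly 5% with equal SDs. All these sizes rest on assumed SDs and correlations, complete data, and fallbacks fitted without the random effect.

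**What to change.** Delete the random-subject-effect wording from SAP VII.F, protocol 9.4.2 and the efficacy table in the protocol synopsis, for the primary and the secondary models. State instead that within-subject correlation is modelled only through the residual matrix (REPEATED with TYPE=UN), as in the example code, and that no random effect is added to the ARH(1) or compound symmetry fallbacks.

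The cost is a few deleted words and one added sentence. SAP I.B allows changes until database lock; the change should be made before unblinding. Nothing is lost, because the unstructured matrix alone covers every covariance that the text model can represent. The stated power is unchanged, since the sample size calculation is a t-test that does not use the MMRM covariance.

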Endpoint	Statistical Analysis Methods
Primary 
 Change from baseline in MADRS total score assessed at 24 hours after the start of the infusion. 	The primary efficacy estimand will be evaluated in the FAS using a mixed effects model for repeated measure (MMRM) analysis with observed cases only. The MMRM model will include fixed effects for treatment, region, visit, study site and treatment by visit interaction, with subject as a random effect and baseline score as a covariate. From this analysis the least squares (LS) mean estimates for each treatment arm at each visit, along with the standard error and 95% confidence intervals (CIs) will be presented separately. The primary comparison for the MADRS is the estimate of the treatment difference at 24 hours after the start of the infusion.
Secondary 
 Change from baseline in MADRS total score at 2 hours, 4 hours, 7 days, and 14 days after the start of the infusion. Proportion of subjects with $\geq 50\%$ improvement in MADRS total score at 24 hours, 7 days, and 14 days after start of infusion. Proportion of subjects with a MADRS total score ≤ 10 at 24 hours, 7 days, and 14 days after start of infusion. Changes in HAM-D on Day 8 and Day 15 after start of infusion. 	Observed and change from baseline values in continuous secondary endpoints will be summarized descriptively by treatment group. Continuous secondary efficacy endpoints assessed at more than 1 postbaseline visit will be analyzed using an MMRM analysis with observed cases only. The MMRM model will include factors for treatment, region, visit, study site, and treatment by visit as fixed effect; subjects as a random effect; and baseline score as a covariate. Categorical secondary endpoints will be summarized by frequency counts and percentages and analyzed by a chi-square test between each PCN-101 dose versus placebo.

Endpoint	Statistical Analysis Methods

 • Change from baseline in QIDS-SR-16 by visit. • Change from baseline in GAD-7 by visit. • Change from baseline in EQ-5D-3L by visit. • Change from baseline in CGI S by visit and CGI I (calculated from predose CGI S). 	
	Alternate sensitivity analyses will be detailed in the SAP.

Abbreviations: CI = confidence interval; MMRM = mixed effects model for repeated measure; SAP = Statistical Analysis Plan.

Safety Analysis

All safety analyses will be performed on the Safety Analysis Set.

Adverse Events

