Secondary	
 To assess the proportion of subjects with a response (defined as $\geq 50\%$ improvement in MADRS total score from predose). 
All secondary efficacy estimands are defined using the same population, ICE strategy, and population level summary (difference in means or proportions between each randomized treatment and placebo, as appropriate) as described above.
 
The variables for the estimands are the following:
 
 MADRS total score assessed at 2 and 4 hours, 7 and 14 days after the start of the infusion (Days 8 and 15, respectively). Note, for the 2-hour and 4-hour recall periods, the sleep and appetite items are not assessed. Proportion of subjects with $\geq 50\%$ improvement in MADRS total score at 24 hours, 7 days, and 14

Objectives	Estimands

 To assess the proportion of subjects with remission (defined as MADRS total score ≤ 10). To define changes in Hamilton Depression Rating Scale (HAM-D). Generalized Anxiety Disorder 7-Item (GAD-7). Clinical Global Impression - Severity (CGI-S) and Clinical Global Impression - Improvement (CGI-I). Quick Inventory of Depressive Symptomatology - 16 Items (QIDS-SR-16). European Quality - 5 Dimensions - 3 Levels (EQ-5D-3L). To determine the safety and tolerability of 2 doses of PCN-101 administered IV in subjects with TRD compared with placebo. 	
days after start of infusion (Days 8 and 15, respectively).
 
 Proportion of subjects with a MADRS total score ≤ 10 at 24 hours, 7 days, and 14 days after start of infusion (Days 8 and 15, respectively). Changes in HAM-D on Day 8 and Day 15 after start of infusion. Change from baseline in GAD-7 by visit. Change from baseline in CGI-S by visit and CGI-I (calculated from predose CGI-S). Change from baseline in QIDS-SR-16 by visit. Change from baseline in EQ-5D-3L by visit. Safety as assessed by: 
 Vital signs 12-lead electrocardiogram (ECG) Oxygen saturation (SpO_2) Clinical laboratory parameters AEs Modified Observer's Assessment of Alertness/Sedation (MOAA/S) Clinician-Administered Dissociative States Scale (CADSS) Brief Psychiatric Rating Scale - Modified 4 Components (BPRS+) 5-Dimensional Altered States of Consciousness Rating Scale (5D-ASC) Columbia Suicide Severity Rating Scale (C-SSRS).

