The primary efficacy endpoint will be based on the change in total MADRS score from baseline at 24 hours after start of infusion.

The MADRS is a ten-item diagnostic questionnaire administered by the study staff to measure the overall severity of depressive symptoms.

The total score is computed as the sum of scores across all 10 items. Higher MADRS score indicates more severe depression. Each item yields a score of 0 to 6, hence the total score ranges from 0 to 60.

$$CMADRS_{total,24hr} = MADRS_{total,24\ hr} - MADRS_{total,Baseline}$$

where

- $CMADRS_{total,24hr}$: Change from baseline in total score MADRS at 24 hours after the start of infusion
- $MADRS_{total,24hr}$: Total score MADRS at 24 hours after the start of infusion

- $MADRS_{total,Baseline}$: Total score MADRS at Baseline

C. Secondary Efficacy Estimand

All secondary efficacy estimands are defined using the same population, intercurrent event strategy, and population level summary (difference in means or proportions between each randomized treatment and placebo, as appropriate) as described in Section VII.A Primary Estimand.

D. Secondary Efficacy Endpoint

Change from baseline in MADRS total score at 2 hours, 4 hours, 7 days, and 14 days after the start of the infusion

The change from baseline MADRS total score will be analyzed for all analysis timepoints.

Since the sleep items will not be assessed at 2 hours and 4 hours after the start of infusion, and the predose scores for these items obtained on the same day will be carried forward.

Proportion of subjects with at least 50% improvement (i.e. reduction) in MADRS total score at 24 hours, 7 days, and 14 days after start of infusion

A subject is considered a responder at a timepoint if a $\geq 50\%$ improvement in MADRS total score (from baseline) is achieved at that timepoint. Any subject who is assessed but not considered as responder at a timepoint will be assumed to be a non-responder at that timepoint.

The proportion of subjects who meet this improvement criterion will be analyzed across different timepoints.

Subjects with MADRS total score ≤ 10 at 24 hours, 7 days, and 14 days after start of infusion will be considered to be in remission

The proportion of subjects who meet this criterion of MADRS total score ≤ 10 will be analyzed across different timepoints. Any subject who is assessed but not considered as remitter at a timepoint will be assumed to be a non-remitter at that timepoint.

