Sensitivity analyses reviewing missing data assumptions will be performed using the same MMRM model specifications as described in [Section VII.F Primary Efficacy Outcome Analysis](#). One analysis will be performed for only the data collected from subjects who were treatment compliant and a separate analysis will be performed with those who completed the study.

In addition, sensitivity analysis exploring the MAR assumptions with multiple imputation of MADRS related endpoints will be performed as described in [Section VII.E Handling of Missing Item Efficacy Endpoint](#). Analysis of each primary and secondary MADRS endpoints will be performed for each of the MI datasets. The analyzed results from the 50 imputed datasets will be combined based on Rubin's rules (Rubin, 1987) using PROC MIANAYLZE in SAS to estimate the pooled analysis results.

H. Secondary Efficacy Analyses

Change from baseline in MADRS total score

Summaries of actual values and changes from baseline score will be presented by treatment group for all analysis timepoints (including 24 hours after start of infusion), beginning with the Baseline visit for the FAS.

Proportion of subjects with $\geq 50\%$ improvement in MADRS total score

For the responder analysis based on a $\geq 50\%$ improvement in MADRS total score at each analysis visit, the proportion of responders will be calculated using frequency counts and percentages, presented for each treatment group.

The response rate between each PCN-101 dose versus Placebo at each analysis visit will be compared using a logistic regression using fixed effects of treatment group, analysis visit, region and treatment group-by-visit interaction. The baseline value will be included as a covariate. Odds ratios (ORs), corresponding two-sided 95% CI and p--values will be derived.

Proportion of subjects with a MADRS total score ≤ 10

The same analysis will be performed as described for the endpoint of proportion of subjects with $\geq 50\%$ improvement in MADRS total score.

Change from baseline in QIDS-SR-16, GAD-7 and EQ-5D-3L

The MMRM model with the same specification as detailed in Change from baseline in MADRS total score will be used to analyze the following secondary efficacy measures for the FAS. Missing data will not be imputed.

- Change from baseline in QIDS-SR-16 by visit
- Change from baseline in GAD-7 by visit
- Change from baseline in EQ-5D-3L VAS by visit

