The adjusted means for each treatment group, pairwise adjusted differences between each treatment group, 95% CI for the differences will be presented at each visit.

Summaries of actual values and changes from baseline scores will be presented by treatment group for each analysis timepoint.

For EQ-5D-3L, frequency counts and percentages of each response to the 5 domains descriptive system will be presented for each treatment group for all analysis visits.

Clinician Global Impression-Severity (CGI-S) and Clinician Global ImpressionChange (CGI-I)

Summaries of actual values and changes from baseline CGI-S scores will be presented by treatment group for each analysis timepoint. Only the actual values of CGI-I will be presented by treatment group for each analysis timepoint.

The observed CGI-S and CGI-I will also be summarized categorically by the number and percentage of subjects reporting each score at each assessment.

The CGI-S and CGI-I scores will be analyzed using the same MMRM model specifications as outlined in the primary efficacy analysis. Since CGI-I cannot be

performed at baseline, the baseline CGI-S score will be used as a covariate in the CGI-I MMRM model.

Model-based point estimates for the difference in adjusted means, 95% CIs and p-values will be reported. Each PCN-101 dose will be compared with placebo. .

I. Secondary Sensitivity Analyses

All inferential statistical analyses as described in [Section VII.H Secondary Efficacy Analyses](#) will be performed with only the data collected from subjects who completed the study. The secondary sensitivity analyses include:

- MMRM model for
 - Change from baseline in QIDS-SR-16
 - Change from baseline in GAD-7
 - Change from baseline in EQ-5D-3L VAS
- Logistic Regression for
 - Proportion of subjects with $\geq 50\%$ improvement in MADRS total score
 - Proportion of subjects with a MADRS total score ≤ 10

The secondary MADRS endpoints will also be analyzed using the multiple imputation approach. The estimates and standard errors of the log (odds ratio) based on the 50 imputed datasets will be combined by applying Rubin's rules to report a pooled result. The combined odds ratio and associated 95% CI and the resulting p-value will be provided.

J. Overview of Inferential Efficacy Analyses

The following [Table 3](#) shows an overview of the types of inferential analyses that will be performed for each efficacy endpoint.

Table 3 Overview of Inferential Efficacy Analyses

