Endpoint	Main	Sensitivity
Primary: Change from baseline MADRS total score	MMRM (observed cases [OC], FAS)	MMRM (MI, complete cases, and treatment compliant cases, FAS)

Secondary: ≥50% improvement in MADRS total score	Logistic Regression (OC, FAS)	Logistic Regression (MI, complete cases and treatment compliant cases, FAS)
MADRS total score ≤ 10	Logistic Regression (OC, FAS)	Logistic Regression (MI, complete cases and treatment compliant cases, FAS)
Change from baseline in QIDS-SR-16, GAD-7 and EQ-5D-3L	MMRM (OC, FAS)	MMRM (complete cases and treatment compliant cases, FAS)
CGI-S, CGI-I score	MMRM (OC, FAS)	MMRM (complete cases and treatment compliant case, FAS)

K. Exploratory Analyses

All descriptive statistics analyses which are performed on the FAS as detailed in [Section VII Efficacy Analyses](#) for the primary and secondary endpoints will be repeated based on the subgroup categories as detailed in [Section V.H Subgroups of Analysis Populations](#).

L. Pharmacokinetics

Not applicable.

VIII. Safety Analyses

All safety related analyses will be performed on the SAS except for the listings of SAEs and AEs leading to death, which will be presented for the FAS.

A. Treatment Exposure and Compliance

Study treatment non-compliance is defined as having an infusion duration with a deviation of more than 5 minutes from the 40 minute infusion time (ie, <35 or >45 minutes of infusion duration).

Exposure to PCN-101 or Placebo will be summarized with descriptive statistics for the following exposure measures.

1. Duration of Treatment (minutes)

- If not interrupted, defined as the time of end of infusion – the time of start of infusion+1
- If interrupted, defined as the (time of end of infusion – the time of start of infusion+1) - (infusion restart time – infusion stop time+1)

Details of the infusion drug administration will be listed by subject.

B. Adverse Events

Adverse events (AEs) will be documented on the AE eCRF and monitored continuously throughout the study. Adverse events will be coded using the Medical Dictionary for Regulatory Activities (MedDRA), version 23.0 or higher, associating lower-level terms with preferred terms and system organ classes by the primary hierarchy. All adverse events will be included in the listings.

Treatment-emergent AEs (TEAEs) are defined as AEs that first occurred or worsened in severity after the start of infusion but no later than the second follow-up visit.

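### Response and remission are defined as differences in proportions, but the SAP plans no confidence interval for a difference; remission has no rule for an arm with no remitters, and HAM-D is missing from the SAP's model lists.

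*SAP*

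**What the plan says.** **Declared effect measure.** SAP VII.C defines the secondary estimands with the "population level summary (difference in means or proportions between each randomized treatment and placebo, as appropriate". Protocol Table 1 has the same words: "population level summary (difference in means or proportions between each randomized treatment and placebo, as appropriate) as described above". For a binary endpoint that means a difference in proportions.

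**Planned analysis.** SAP VII.H gives response a descriptive display, in which "the proportion of responders will be calculated using frequency counts and percentages, presented for each treatment group". It then has the rates "compared using a logistic regression using fixed effects of treatment group, analysis visit, region and treatment group-by-visit interaction", with baseline as a covariate, and reports "Odds ratios (ORs), corresponding two-sided 95% CI" and p-values. Remission gets the same analysis. Under multiple imputation (VII.I), "The estimates and standard errors of the log (odds ratio) based on the 50 imputed datasets will be combined" by Rubin's rules. The sensitivity entry for both endpoints in Table 3 is "Logistic Regression (MI, complete cases and treatment compliant cases, FAS".

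**Fallbacks.** SAP VII.F names alternative covariance structures if the MMRM does not converge, and VII.E allows changes to the imputation models. Neither covers the logistic regression.

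**HAM-D.** Protocol 9.4.2 lists HAM-D among the scores to be analysed with the MADRS model approach. SAP Table 1 has it as a secondary endpoint at Day 8 and Day 15, and VII.D says only that its change is analysed by timepoint. VII.H, VII.I and Table 3 do not mention it, although QIDS-SR-16, GAD-7, EQ-5D-3L, CGI-S and CGI-I are all given an MMRM.

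**The concern.** There are three gaps, all in secondary endpoints.

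1. The quantity that the estimand names gets no interval. A reader can subtract two percentages, but the plan does not say how precise the result is, and a covariate-adjusted odds ratio cannot be turned back into that difference without a placebo rate.
2. Remission at 31 per arm can be sparse. With a treatment-by-visit interaction, an arm with no remitters at a visit has no finite odds ratio there. If that arm is placebo, both dose comparisons at the visit are lost. Any imputed dataset in which the arm stays empty also has no finite log odds ratio to pool. If no rule is added before unblinding, the substitute method would be chosen with the result in view, and plausible substitutes can disagree.
3. HAM-D could lose its protocol model simply because tables are programmed from the SAP.

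**Working it through.** **Inputs from the documents.** 31 subjects per arm, a difference of 8 MADRS points, SD 11, two-sided alpha 0.05 (SAP III.C). The documents state no response or remission rate, so every rate below is an assumption.

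**The plan's own figure.** For a two-sample t-test with 60 df, the noncentrality is 8 / (11 × √(2/31)) = 2.86 and the power is 80.4%. The stated 80% is reproduced. It concerns the primary endpoint only.

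**Odds ratio versus difference.** For placebo rate p and odds ratio OR, the active rate is q = OR·p / (1 − p + OR·p). With OR = 3:

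| Placebo rate | Active rate | Difference |
|---|---|---|
| 5% | 13.6% | 8.6 points |
| 10% | 25.0% | 15.0 points |
| 20% | 42.9% | 22.9 points |

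**Width of the missing interval for response.** Assume baseline MADRS with mean 33 and SD 5, placebo change −9, and 30% US subjects, with the plan's 8-point effect and SD 11. Response is then 25.1% versus 51.7%.

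- Unadjusted SE: √(0.251 × 0.749/31 + 0.517 × 0.483/31) = 11.9 points.
- In 4,000 simulated trials at one visit, standardising from a logistic model with treatment, region and baseline gave a mean SE of 11.5 points, so the 95% CI is about ±1.96 × 11.5 = ±22.5 points.
- The empirical SD was 11.9 and coverage 93.1%. No fit failed.

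**Chance of an empty arm at one visit.** P(0 of 31) = (1 − p)^31:

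| True rate | P(0 of 31) |
|---|---|
| 3% | 39% |
| 5% | 20% |
| 8% | 7.5% |
| 10% | 3.8% |
| 15% | 0.65% |
| 25% | 0.013% |

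It equals 5% at p = 1 − 0.05^(1/31) = 9.2%. Response, at an assumed 25%, is not exposed; remission may be.

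**What the planned model does with an empty placebo arm.** A hypothetical 6/31 versus 0/31 at 24 hours was fitted with the treatment-by-visit logistic model, leaving out region and baseline. The log odds ratio was 10.1, 25.1 and 34.1 when iteration was stopped at 10, 25 and 50; the SE reached about 5.8 million and the Wald p about 1.0. Fisher's exact p for the same table is 0.024.

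**How far substitutes can differ.** Hypothetical 5/31 versus 0/31:

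- Uncorrected chi-square p = 0.020 (two expected counts of 2.5); Fisher's exact p = 0.053.
- Firth log odds ratio 2.571, so OR 13.1. Profile-penalised 95% CI 1.4 to 1,746. With SE 1.52, the Wald 95% CI is 0.66 to 259 (p = 0.09).
- Difference 16.1 points, Miettinen-Nurminen 95% CI 4.1 to 32.8.
- Firth-standardised difference 15.6 points, SE 7.1.

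**Coverage of the interval proposed for remission.** Exact coverage of the 95% Miettinen-Nurminen interval, 31 per arm, at active/placebo rates of 10/3%, 15/5%, 20/8% and 25/10%, is 95.6%, 94.1%, 94.8% and 94.7%.

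**The case against.** **Odds ratios are not foreign to the protocol.** Protocol 9.4.2 plans odds ratios with 95% CI for binary endpoints. This stands, with a limit: that sentence concerns exploratory endpoints, whereas response and remission are secondary. The label may be a slip. If so, the mismatch with the estimand starts inside the protocol; it is not removed.

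**A reader might infer an unresolved conflict of tests**, since the protocol synopsis has categorical secondary endpoints "analyzed by a chi-square test between each PCN-101 dose versus placebo". The documents do not support that. SAP I.B makes the SAP the governing document, and Protocol 9.4.2 leaves full details to it, so logistic regression applies.

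**A reader might infer that a post hoc choice is inevitable, or that response is at risk too.** Neither follows. SAP I.B allows changes until database lock, so a rule can still be set while blinded. The empty-arm risk rests on assumed rates, is small above about 10%, and affects only the visit concerned.

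**A reader might infer that HAM-D has no planned model at all.** Protocol 9.4.2 plans one. SAP VII.D also uses the same by-timepoint wording for QIDS-SR-16 and GAD-7, which do get an MMRM. This looks like a drafting omission.

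**Any reader can build an unadjusted interval from the tabulated counts.** That is true, but the method would not be pre-specified, and the planned region and baseline adjustment would be lost for response. These endpoints also carry no multiplicity control in a proof-of-concept trial, which limits the weight of the point without closing the gap.

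**Conclusion.** The point holds, for secondary endpoints only. The difference in proportions is declared as the effect measure, yet the plan gives it no confidence interval; this does not depend on any assumed rate. Under the assumptions above, the missing interval for response would be about ±22.5 points, wide enough that readers need to see it.

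For remission there is also no rule for an empty arm. The chance of one at a visit is 5% or more only if the true rate is about 9% or lower, and the documents give no rate to judge that by.

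HAM-D's protocol model has not been carried into the SAP. The primary MMRM on MADRS at 24 hours is not affected. The changes are worth making before database lock.

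**What to change.** 1. **Differences in proportions (VII.H).** At 24 hours, Day 8 and Day 15, report each dose's difference versus placebo with a 95% CI, and keep the odds ratios as supportive.
   - Response: standardise from a logistic model fitted at each visit with treatment, region and baseline. Note the slight under-coverage at 31 per arm (about 93% in simulation).
   - Remission: use the unstratified Miettinen-Nurminen interval, which stays defined with an empty arm. State that it is unadjusted for region and baseline.
2. **Remission odds ratio.** Specify in advance a Firth-penalised logistic model by visit (treatment, region, baseline MADRS), with a profile-penalised CI in the observed-case analysis.
3. **Multiple imputation (VII.I).**
   - Pool the Firth log odds ratios and their standard errors by Rubin's rules. Label the resulting interval as Wald-type and supportive, because it can disagree with the profile interval in sparse data: in the 5/31 versus 0/31 example, one includes 1 and the other does not.
   - Pool the differences and their standard errors in the same way. Take the remission difference from the Firth model by standardisation, so that its standard error is defined with an empty arm.
4. **HAM-D.** Add change from baseline to the MMRM lists in VII.H, VII.I and Table 3, with differences versus placebo and 95% CI at Day 8 and Day 15.

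The cost is SAP wording and modest programming, with no new data. The downside is that the observed-case remission difference is not covariate-adjusted.
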